 5. Delirium
 6. Septic Shock
2. Postoperative ICU admission (yes/no)
3. Prolonged Postoperative Length of Stay (LOS) (greater than vs. less than or equal to CIHI Expected Length of Stay (ELOS) as assigned by the Case Mix Grouping) [note that the LOS includes the day of surgery]
4. Hospital readmission within 30 days (yes/no)
5. Intraoperative mortality (yes/no)
6. Days alive and out of hospital at 30 days postoperatively (28)

III. Other predictors included into model

The following potential perioperative predictors will be evaluated as covariates during model building. Statistically significant predictors will be retained in the model.

Table 2. Other predictors

Preoperative	
 1. Demographics: age on date of surgery, sex, obesity (body mass index>30) 2. Indicators of preoperative comorbidities: since no comorbidity score has perfect performance, a variety of models will be evaluated and the most significant predictive score will be retained in the model. 
 • American Society of Anesthesiologist class • RCRI score(29), and specific components via ICD codes (history of ischemic heart disease, congestive heart failure, cerebrovascular disease, diabetes, chronic kidney disease, and CCI and Case Mix Group codes of suprainguinal vascular, intraperitoneal, or intrathoracic surgery) using previously published methods (30)(31) • Elixhauser comorbidity index (32) and Charlson Comorbidity Index (33): calculated using diagnoses from the previous three years according to standard algorithm by HDNS. Reported as both total score and individual categories • Hospital Frailty Risk Score (34): based on ICD codes • Preoperative blood pressure: ICD diagnosis of hypertension and by measured blood pressure • Preoperative heart rate: Innovian and HSM • Chronic Obstructive Lung Disease (ICD code): since it may affect the interpretation of results of SpO₂ and EtCO₂ 3. Indicators of surgical complexity 
 • CIHI DAD Case Mix Group (CMG) class (also contains categories that include medical complexity) • Main Surgical Service • Procedural Index for Mortality Risk (PIMR) (35): according to CCI • Procedure: CCI codes • Preoperative ICU admission • Emergency surgery: as determined by DAD Method of Entry = emergency department or transferred from another institution)

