CIHI DAD	PATIENT_ID: encrypted health card number For HDNS internal use	Patient	Jan 1, 2013 to Dec 1, 2017	HDNS data linkage with Innovian-HSM. The dataset given to us will not contain Patient_ID, but rather a Study ID.
Vital Statistics	PATIENT_ID: encrypted health card number For HDNS internal use	Patient	Jan 1, 2013 to Dec 1, 2017	HDNS data linkage with Vital Statistics. The dataset given to us will not contain Patient_ID, but rather a Study ID.
CIHI DAD	PDATE[1-n]: procedure date	Patient	Jan 1, 2013 to Dec 1, 2017	HDNS data linkage with Innovian surgery date, to ensure that only the admission corresponding to the surgery admission of interest (first surgery admission with LOS>1) is included.

				
The PDATE matching the date of procedure (+/- 1 day) from Innovian will be used. The corresponding number (e.g. PDATE1) will be used for all procedure-related codes (e.g. PCODE1, PDSERV1).
 
Note that except for preoperative comorbidity data, where we would need data for 3 years prior to PDATE, for all other variables we only need data within 30 days after PDATE.

CIHI DAD	
LOS: Length of Stay (after surgery)
 
Derived by HDNS: discharge date minus PDATE + 1 (includes day of surgery)
	Patient	
Jan 1, 2013 to Dec 1, 2018 (to account for prolonged LOS postop from the end of inclusion date)
	
Part of inclusion criteria: if a patient had multiple surgeries, the first surgery with a LOS >1 (i.e. at least overnight stay). To calculate ratio of LOS to Expected Length of Stay (ELOS) as secondary outcome. We have chosen to standardize LOS to only include duration of stay after surgery, since there are many factors that may prolong a patient's stay prior to surgery.

Additional Demographic Information				
CIHI DAD	SEX: Patient sex	Patient	
Jan 1, 2013 to Dec 1, 2017
	
As sex may affect outcomes, this will be included as a covariate in our models
 
M = Male
 
F = Female

HSM	BMI: Body Mass Index [Derived by Innovian]	Patient	
Jan 1, 2010 to Dec 1, 2017
	
Dichotomized according to WHO definition for obesity: BMI>30. This will be combined with ICD code to create a binary Obesity variable (please see below).

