CIHI DAD	Obesity [Derived by HDNS]	Patient	Jan 1, 2010 to Dec 1, 2017	Binary variable (yes/no), “yes” defined by: BMI >30, and if BMI missing, obesity ICD code (DXCODE[1-n] = E66). As BMI may affect outcomes, this will be included as a covariate in our models. The BMI data from HSM-Innovian will take precedent over DXCODE: i.e. first identify patients BMI>30 (coded as obesity = yes), BMI <=30, and BMI=missing data. For patients with BMI=missing, patients with ICD E66 will also be coded as obesity = yes.
Additional Measures of Perioperative Comorbidity				
CIHI DAD	DXCODE [1-n]: diagnosis code	Patient	Jan 1, 2010 to Dec 31, 2017 (3 years before and including 30 days after date of surgery)	Diagnosis codes are required for the following purposes: 
 HDNS will use DXCODE (with “DXTYPE[1-n] = 1”, OR “DXTPRE[1-n] = 2 AND DXPRE[1-n] = 5”, OR “DXTYPE[1-n] = 3 AND DXPRE[1-n] = 5”, OR “DXTYPE[1-n] = M AND DXPRE[1-n] = 5”) within three years before date of surgery to calculate the Elixhauser comorbidity index, Charlson Comorbidity Index, RCRI, and Hospital Frailty Risk Score (see below). The entirety of DXCODES do not need to be disclosed to the research team since HDNS will perform the calculations. Specific comorbid conditions will be included as covariates in the analysis To examine post-operative comorbidity

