HSM	Preoperative insulin use (yes/no) [Derived by Innovian: yes = any insulin use in the preoperative medication list]	Patient	3 years before and including date of surgery (i.e. Jan 1, 2010 to Dec 1, 2017)	Due to the difficulty of obtaining this data from ICD codes (the code for this, Z79.4, only came to existence in 2018), this will help identify patients on insulin for the RCRI score.
Innovian (from linked lab database)	Preoperative Creatinine ($\mu\text{mol/L}$)	Patient	3 years before and including date of surgery (i.e.	This will help identify patients who satisfy the chronic kidney disease category (Pre-operative creatinine $>176.8 \mu\text{mol/L}$) to calculate the RCRI score.

			Jan 1, 2010 to Dec 1, 2017)	
CIHI DAD	HFRS: Hospital Frailty Risk Score [Derived by HDNS]	Patient	3 years before and including date of surgery (i.e. Jan 1, 2010 to Dec 1, 2017)	As the HFRS has been shown to affect outcomes, it will be included as a covariate. HDNS will calculate using DXCODE according to a published protocol (34). Detailed protocol will be sent to the HDNS.
Innovian and HSM	Preoperative mean arterial pressure (MAP) [Derived by Innovian]	Patient	Jan 1, 2013 to Dec 1, 2017	As preoperative high blood pressure may affect the interpretation of the threshold of harm for intraoperative blood pressure (12), preoperative MAP will be used in the calculation of change in MAP (absolute and %). HSM contains blood pressure of elective surgery patients at the anesthetic clinic and prior to entering the operating room, while Innovian contains the first blood pressure of all patients in the operative room. The lowest blood pressure from either Innovian or HSM will be used.
HSM	Preoperative systolic blood pressure (SBP) [Derived by Innovian]	Patient	Jan 1, 2013 to Dec 1, 2017	As preoperative high blood pressure may affect the interpretation of the threshold of harm for intraoperative blood pressure (12), preoperative SBP will be used in the calculation of change in SBP (absolute and %). HSM contains blood pressure of elective surgery patients at the anesthetic clinic and prior to entering the operating room. The first Innovian blood pressure will be used for emergency surgery patients, since HSM pressure will not be available.

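### Measured BMI enters the models only as an obesity flag, and measured creatinine only through one RCRI item; both should also be offered as continuous covariates

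*Combined protocol and SAP*

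**What the plan says.** **BMI.** The BMI row of Appendix 1 (source HSM) reads "Dichotomized according to WHO definition for obesity: BMI>30". Table 2 lists the demographic covariates as "age on date of surgery, sex, obesity (body mass index>30"; BMI itself is not there. The Obesity row gives the reason for adjustment, "As BMI may affect outcomes, this will be included as a covariate in our models", and a fallback: "For patients with BMI=missing, patients with ICD E66 will also be coded as obesity = yes".

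**Creatinine.** Appendix 1 requests preoperative creatinine in µmol/L from the linked laboratory database, over the three years up to and including the day of surgery. The stated purpose is "This will help identify patients who satisfy the chronic kidney disease category", that is, the RCRI item above 176.8 µmol/L. Table 2 has no creatinine covariate.

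**Medication list.** The HSM preoperative medication list yields one derived variable, "yes = any insulin use in the preoperative medication list", and its purpose is also the RCRI: "this will help identify patients on insulin for the RCRI score".

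**Related rules.** The Hypothesis section frames the primary question as an association after control for other predictors. Under Creating the models, splines are planned only for hemodynamic predictors measured in time. Under Missing data, an absent ICD code counts as no disease. Other variables are left unprocessed below 5% missing, filled with the group mean at 5–20% if continuous, and dropped above 20%.

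**The concern.** Body size and renal function are plausible determinants of both intraoperative hemodynamics and death, and the plan itself says BMI may affect outcomes. With a single cut at 30, a severely underweight patient gets the same code as one with BMI 29. The creatinine item likewise scores 60 and 170 µmol/L alike.

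Creatinine may also fail to reach the model at all. Table 2 lets several comorbidity scores compete and keeps the most significant one. If the Elixhauser or Charlson index is kept and the RCRI kidney component is not, the laboratory value contributes nothing.

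Two things are at stake. One is residual confounding in the hemodynamic associations. The other is some loss of predictive information in a model meant to outperform the Surgical Apgar Score. The Limitations section accepts that unknown confounders may remain, but these two are known and measured.

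**Working it through.** **1. The plan's own figure.** From Power calculation: 1.7% mortality, 24,000 patients in the derivation group, 10 events per predictor.
- Events: 0.017 × 24,000 = 408.
- Predictors: 408 / 10 = 40.8, stated as 41. Both figures reproduce.

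**2. What the cut saves in parameters.** A flag costs 1 df, a linear term 1 df, and a restricted cubic spline with 3 or 4 knots 2 or 3 df.
- Replacing the obesity flag by linear BMI costs nothing extra. A linear creatinine term costs 1 df where no renal term is otherwise in the model.
- Splines for both add about 2 to 5 df. On a full 41-predictor model, events per predictor go from 408/41 = 9.95 to 408/43 = 9.49 (2 extra) or 408/46 = 8.87 (5 extra).
- Table 1 alone lists 9 (SBP) + 11 (MAP) + 9 (heart rate) + 5 (medications) + 4 (SpO₂) + 4 (EtCO₂) = 42 exposure variables, or 408/42 = 9.71 events each. The candidate set already exceeds 41, so the cuts do not keep it within the limit.

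**3. Information kept by a cut.** For a normal covariate with a linear effect, and a share p above the cut at z, the fraction kept is φ(z)² / [p(1 − p)]. The documents do not give p, so the ranges below are assumed.

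| Cut | p (assumed) | φ(z) | Kept |
|---|---|---|---|
| BMI > 30 | 0.25 | 0.3178 | 0.54 |
| BMI > 30 | 0.40 | 0.3863 | 0.62 |
| Creatinine > 176.8 | 0.02 | 0.0484 | 0.12 |
| Creatinine > 176.8 | 0.05 | 0.1031 | 0.22 |

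For creatinine, the normal and linear assumptions are best read on the log scale.

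**4. What that can do to an adjusted association.** This is an illustration, not an estimate for this cohort. One million patients were simulated per setting, with about 1.7% deaths, a binary exposure with true OR 1.00, and an assumed log-OR of 0.5 per SD of the covariate on both exposure and death.
- Unadjusted exposure OR: 1.24–1.31.
- Adjusted for a flag with 30–40% above the cut: 1.08–1.13.
- Adjusted for a flag with 3–5% above the cut: 1.17–1.19.
- Adjusted for the continuous value: 0.98–1.03, which is 1.00 within simulation error.
- C-statistic of the covariate alone: 0.59–0.60 (30–40% above) or 0.53–0.54 (3–5% above) as a flag, against 0.64 as a continuous value.

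**5. Is the information used elsewhere?** No section uses BMI or creatinine more fully. Partial substitutes are the Elixhauser renal failure, weight loss and obesity categories, the Charlson renal disease category, the Hospital Frailty Risk Score and ASA class. The coded categories are yes/no, and an absent code is read as no disease.

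**The case against.** The strongest reply is that the obesity flag does a job that continuous BMI cannot. It survives a missing BMI through the E66 code. For blood pressure and heart rate, the plan says only some patients have HSM values; it does not give BMI completeness. Under the Missing data rule, continuous BMI could be mean-imputed or dropped. This stands. It means the change needs its own missing-value rule, but it is not a reason to discard BMI where it was measured.

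A second reply is that the predictor budget is already overspent. That is true, but linear terms cost little, and LASSO or elastic net selection is planned anyway.

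Some stronger readings are tempting, and the documents do not support them:

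- *The cuts save nothing.* This holds for parameters if linear terms are used. It ignores the E66 fallback and the extra df of splines.
- *The models treat all creatinine values below 176.8 alike.* This is true of the RCRI item. The models also have coded renal categories, and creatinine is requested as a number; the gap is its absence from Table 2.
- *Chronic rate- and pressure-lowering drugs are already extracted and must be forced in.* Appendix 1 describes only a derived insulin flag. Other drug flags would be new derivations at 1 df each. Coded cardiac conditions and measured preoperative blood pressure and heart rate already capture part of their effect.
- *Predictive performance will suffer greatly.* The documents give no BMI distribution or effect. Under an assumed U-shaped BMI risk with 24,000 patients, beside other predictors giving a C-statistic of about 0.83, a BMI spline raised the in-sample C-statistic by only about 0.002–0.006.

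**Conclusion.** The point holds for BMI and creatinine: the plan obtains both as measurements and gives neither a continuous role in the models. Existing covariates make up only part of the loss. The 54–62% (BMI) and 12–22% (creatinine) figures assume normality, a linear effect and the stated shares above each cut. A U-shaped BMI effect would change the BMI figure. The effect on the primary result cannot be computed from the documents. The stronger ground for change is confounding control; the gain in discrimination may be small. This is an inexpensive improvement to make before modelling, and it does not invalidate the plan. Drug flags beyond insulin are optional.

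**What to change.** - Add continuous BMI and log creatinine to Table 2 as candidate covariates, each linear or as a low-df restricted cubic spline, with the form fixed in advance.
- Keep the obesity flag for description, and the 176.8 µmol/L cut for computing the RCRI.
- State which creatinine value in the three-year window is used, for example the last before surgery.
- Give both variables their own missing-value rule, so that group-mean filling or removal does not apply by default. For BMI the rule should keep the E66 information, for example by a missing-BMI indicator or imputation informed by E66. Report completeness separately for elective and emergency patients.
- Optionally, ask whether the medication list can yield flags for other rate- or pressure-lowering drugs. Offer these as candidates; they need not be forced in.

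Cost: no new data source for BMI and creatinine, about 2–5 df if both are splined, and missing values to handle for some patients. The drug flags would need a further derivation by the data holder.

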			
Comorbidity covariates: We need the following DXCODE (with “DXTYPE[1-n] = 1”, OR “DXTPRE[1-n] = 2 AND DXPRE[1-n] = 5”, OR “DXTYPE[1-n] = 3 AND DXPRE[1-n] = 5”, OR “DXTYPE[1-n] = M AND DXPRE[1-n] = 5”) within 3 years before PDATE: Disease categories for RCRI (please see “RCRI”); hypertension (I10-I15), COPD (I27.8, I27.9, J40.x–J47.x, J60.x–J67.x, J68.4, J70.1, J70.3), Obesity (E66)
 
Postoperative outcomes: We need the following DXCODE (with “DXTYPE [1-n]=2” Excluding “DXTYPE [1-n]=2 AND DXPRE [1-n]=5”, OR “DXTYPE [1-n]=3” excluding “DXTYPE [1-n]=3 AND DXPRE [1-n]=5”, OR “DXTYPE[1-n] = M AND DXPRE[1-n] = 6”) to include into model as individual, categorical, and composite secondary outcome:
 
Cardiac: acute myocardial infarction (I21 to I22, I24), cardiac arrest (I46.0, 146.1, I46.9), ventricular tachycardia (I47.2), shock (R57, T81.1) excluding septic shock (R57.2), congestive heart failure (I50.0, I50.1, I50.9), pulmonary edema (J81), complete heart block (I44.2)
 
Respiratory: pneumonia (J13 to J18, J69.0, J69.8, J95.4), pulmonary embolism (I26), acute respiratory failure (J95.1, J95.2, J96.0), respiratory arrest (R9.2)

--	--	--	--

				
Cerebrovascular: strokes and transient ischemic attacks (I60 to I69, G45)
 
Delirium (F5)
 
Acute kidney injury (N17)
 
Septic shock (R57.2)

CIHI DAD	DXPRE [1-n]: diagnosis prefix	Patient	Jan 1, 2010 to Dec 31, 2017 (3 years before and including 30 days after date of surgery)	
To categorize the type of the corresponding DXCODE (please see above):
 
C = Cause of death Q = Query Diagnosis/Etiology 5 = Comorbidity arose before qualifying intervention 6 = Comorbidity arose during or after qualifying intervention 8 = Palliative Care

CIHI DAD	DXTYPE [1-n]: diagnosis type	Patient	Jan 1, 2010 to Dec 31, 2017 (3 years before and including 30 days after date of surgery)	
To categorize the type of the corresponding DXCODE (please see above):
 
M = Most Responsible Diagnosis 1 = Pre-admit comorbidity 2 = Post-admit comorbidity 3 = Secondary Diagnosis

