CIHI-DAD	Admit-date	Patient	1Jan2010 to 31Dec2017	
For 3-year look-back window with: either admission date or discharge date is between surgery date (B) and 3 years before B (A), assuming that A<B.
 
For 30-day follow-up window with: Either admission date or discharge date is between surgery date (B) and 30 days after B (C), assuming that B<C.

CIHI-DAD	Discharge_date	Patient	1Jan2010 to 31Dec2017	For 3-year look-back window with: either admission date or discharge date is between surgery date (B) and 3 years before B (A), assuming that A<B.

				For 30-day follow-up window with: Either admission date or discharge date is between surgery date (B) and 30 days after B (C), assuming that B<C.
CIHI DAD	ECI: Elixhauser comorbidity index [Derived by HDNS]	Patient	Jan 1, 2010 to Dec 1, 2017 (3 years before and including date of surgery)	
To be computed by the HDNS according to protocol (32) using DXCODES (please see above), to be included into model as covariate. Please report both total score, and any of the following individual categories:
 
Congestive heart failure Cardiac arrhythmias Valvular disease Pulmonary circulation disorders Peripheral vascular disorders Hypertension, uncomplicated Hypertension, complicated Paralysis Other neurological disorders Chronic pulmonary disease Diabetes, uncomplicated Diabetes, complicated Hypothyroidism Renal failure Liver disease Peptic Ulcer Disease Excluding Bleeding AIDS/HIV Lymphoma Metastatic cancer Solid tumor without metastasis Rheumatoid arthritis/ collagen vascular diseases Coagulopathy Obesity Weight loss Fluid and electrolyte disorders Blood loss anemia Deficiency anemia Alcohol abuse Drug abuse Psychoses

				Depression

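### The look-back drops type M, 2 and 3 diagnoses without prefix 5 even from admissions that ended before surgery, and the morbidity rule counts type 2 and 3 codes without evidence of postoperative onset

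*Combined protocol and SAP*

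**What the plan says.** Appendix 1 (DXCODE row) uses hospital diagnosis codes "within three years before date of surgery to calculate the Elixhauser comorbidity index, Charlson Comorbidity Index, RCRI, and Hospital Frailty Risk Score". A code qualifies if it is type 1, with no prefix condition, or if it meets one of three further clauses: "DXTPRE[1-n] = 2 AND DXPRE[1-n] = 5", "DXTYPE[1-n] = 3 AND DXPRE[1-n] = 5" or "DXTYPE[1-n] = M AND DXPRE[1-n] = 5". The same filter is written out again for the individual covariates, including hypertension and COPD.

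The admission-date and discharge-date rows define the look-back as any admission for which "either admission date or discharge date is between surgery date (B) and 3 years before B (A"), so earlier admissions and the index admission both enter. The 30-day follow-up is built the same way: "Either admission date or discharge date is between surgery date (B) and 30 days after B (C"). No date for an individual diagnosis is listed.

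The keys define prefix 5 as onset before a qualifying intervention, and give "6 = Comorbidity arose during or after qualifying intervention". Type 1 is a pre-admission and type 2 a post-admission condition. Type 3 is only "3 = Secondary Diagnosis".

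For postoperative morbidity, type M counts only with prefix 6. Types 2 and 3 count unless they carry prefix 5.

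Two places in the main text bear on this. Missing data treats a patient without a code as free of the disease. Table 2 says that Elixhauser and Charlson use three years of diagnoses and a standard algorithm, and mentions no type or prefix restriction.

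**The concern.** A timing prefix separates before from after within an admission that contains the operation of interest. On an admission discharged before the index surgery there is nothing left to separate, because every diagnosis on it is preoperative. The filter nevertheless discards, for example, a most responsible diagnosis of heart failure with a blank prefix, or a stroke that complicated an earlier operation and carries prefix 6. If the condition appears nowhere else in a qualifying form, the patient is coded as never having had it.

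The hypothesis is about associations after control for other predictors, and the comorbidity scores supply part of that control, in the mortality models too. RCRI, frailty and preoperative hypertension also define subgroups.

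On the outcome side, the plan asks for positive evidence of timing for type M but not for type 3, whose definition carries no timing, nor for type 2, which means after admission and not necessarily after surgery. Disease present before the operation can therefore be counted as a complication of it.

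**Working it through.** **1. The two filters as rules.** I read the undefined field name in the type 2 clause as DXTYPE and crossed the four listed types with six prefix states. C = counts as comorbidity, O = counts as postoperative outcome, – = neither.

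| Type | blank | 5 | 6 | Q | C (cause of death) | 8 (palliative) |
|---|---|---|---|---|---|---|
| 1 | C | C | C | C | C | C |
| M | – | C | O | – | – | – |
| 2 | O | C | O | O | O | O |
| 3 | O | C | O | O | O | O |

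Of 24 cells, 9 are comorbidity, 11 outcome, 4 neither and none both.

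- Look-back: all 6 type 1 cells are kept. Of the 18 cells for types M, 2 and 3, 15 are dropped, including every blank and every prefix 6, whatever admission they come from.
- Outcomes: 5 of 6 type 3 cells and 5 of 6 type 2 cells count. Only prefix 6 shows onset during or after an intervention.
- On the index admission, a pre-existing heart failure code of type 3 with a blank prefix is scored as a cardiac complication and that entry is not counted as comorbidity.
- Taken literally, the undefined field name would leave type 2 with prefix 5 in neither group.

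**2. Illustration for the covariates.** The documents give no share of diagnoses lost, so every input here is assumed: condition prevalence 20%; OR 2.5 for death; exposure 45% with and 25% without the condition; true exposure OR 1.00; no false positives; mortality 1.3% without the condition.

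- Odds of death with the condition: 2.5 × 0.013/0.987 = 0.0329, so risk = 0.0329/1.0329 = 3.19%. Overall mortality: 0.20 × 3.19% + 0.80 × 1.30% = 1.68%, close to the plan's 1.7%.
- With 50% captured, the patients recorded as free of the condition include 0.20 × 0.50 = 0.10 of the cohort who have it and 0.80 who do not.
- Share truly affected among the exposed: 0.10 × 0.45/(0.10 × 0.45 + 0.80 × 0.25) = 0.045/0.245 = 18.4%. Among the unexposed: 0.10 × 0.55/(0.10 × 0.55 + 0.80 × 0.75) = 0.055/0.655 = 8.4%.
- Risks: 0.184 × 3.19% + 0.816 × 1.30% = 1.65%, against 0.084 × 3.19% + 0.916 × 1.30% = 1.46%. The OR in this stratum is 1.13. In the stratum recorded as affected it is 1.00.
- A logistic model with exposure and the recorded condition, fitted to the exact cell probabilities, combines the two strata:

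| Share captured | 100% | 70% | 50% | 30% |
|---|---|---|---|---|
| OR, recorded-free stratum | 1.00 | 1.09 | 1.13 | 1.16 |
| Adjusted exposure OR | 1.00 | 1.06 | 1.10 | 1.14 |

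Baseline risks from 1% to 5% change the adjusted ORs by less than 0.01.

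**3. Illustration for morbidity.** Assume true morbidity r = 5%, all of it flagged, and a share x of the other patients carrying a preoperative outcome code that the rule counts. Observed = r + (1 − r)x; share of flagged cases that are true = r/observed.

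| x | Observed | True among flagged |
|---|---|---|
| 0.5% | 0.05 + 0.95 × 0.005 = 5.5% | 91% |
| 1% | 0.05 + 0.95 × 0.01 = 6.0% | 84% |
| 2% | 0.05 + 0.95 × 0.02 = 6.9% | 72% |
| 5% | 0.05 + 0.95 × 0.05 = 9.8% | 51% |

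**The case against.** The strongest reply is that type 1 rescues much of what the filter drops. A chronic condition coded as pre-admission comorbidity on the index admission, or on any other admission in the three years, is kept without a prefix. This stands. A reader might infer that comorbidities on earlier admissions are lost unless coded as arising before an intervention; the first clause of the filter rules that out. Only conditions that appear solely as type M, 2 or 3 without prefix 5 are lost.

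Other measures give partial protection. RCRI also uses insulin from HSM, laboratory creatinine and procedure codes; obesity uses measured BMI first; measured blood pressure stands beside coded hypertension; ASA class does not come from these codes. This limits the harm but does not restore ischemic heart disease, heart failure, cerebrovascular disease or COPD to the coded variables.

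The prefix 6 example is narrow, because the index is the first eligible operation since January 2013. For surgery from 2016 onward, the earlier operation must have been elsewhere, cardiac, without an overnight stay or otherwise ineligible. The blank type M code does not have this limit.

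The key does not say whose intervention the prefix refers to, and the meaning and frequency of a blank depend on coding rules outside the documents. That is a reason to claim no size. It does not rescue the look-back rule, because the discharge date alone shows that such diagnoses are preoperative.

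The Limitations section concedes possible misclassification in general terms, but not this rule, which can be corrected before derivation.

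**Conclusion.** The point holds in two limited parts. In the look-back, a stated rule gives wrong covariate values for patients whose condition is recorded only as type M, 2 or 3 without prefix 5 on an admission that ended before surgery. It also sits uneasily with Table 2's description of Elixhauser and Charlson. In the morbidity outcomes, type 2 and 3 codes with a blank or query prefix count without evidence of postoperative onset.

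A reader might infer that the primary outcome is contaminated as well. It is not: 30-day death comes from Vital Statistics, and the mortality models are touched only through their covariates. Nor do the documents show that blank or query codes are common.

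The size cannot be computed from the documents. The ORs of 1.06, 1.10 and 1.14 rest wholly on assumed inputs and a single confounder with no proxies. They are an upper illustration for those inputs, because age, ASA class and overlapping indices are also candidate covariates. The point is worth correcting because the correction is specific and cheap, not because a large bias has been shown.

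**What to change.** In the derivation specification for HDNS:

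- Apply the type/prefix rule to the index admission only.
- For admissions discharged before PDATE, accept types M, 1, 2 and 3 with prefix 5, 6 or blank, and exclude Q. State how prefixes C and 8 are handled.
- Correct the field name in the type 2 clause to DXTYPE, and align Table 2 with Appendix 1.
- For morbidity, exclude Q, tabulate type 2 and 3 outcome codes by prefix, and report results with prefix 6 required for both types alongside the current rule.

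The cost is a change in the HDNS derivation code and one extra analysis. Requiring prefix 6 may lose true complications with a blank prefix. Their number is unknown, which is why the two rules should be reported side by side, with the prefix table to show how far they can differ.
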